6.3 Lost to Follow-up

A patient will be considered lost to follow-up if they repeatedly fail to return for scheduled visits and is unable to be contacted by the study site.

The following actions must be taken if a patient fails to return to the clinic for a required study visit:

- The site must attempt to contact the patient and reschedule the missed visit as soon as possible and counsel the patient on the importance of maintaining the assigned visit schedule and ascertain whether or not the patient wishes to and/or should continue in the study.
- Before a patient is deemed lost to follow-up, the Investigator or designee must make every effort to regain contact with the patient (where possible, 3 telephone calls and, if necessary, a certified letter to the patient's last known mailing address or local equivalent methods). These contact attempts should be documented in the patient's medical record.
- Should the patient continue to be unreachable, they will be considered to have withdrawn from the study.

7 STUDY ASSESSMENTS AND PROCEDURES

- Study procedures and their timing are summarized in the SoA. Protocol waivers or exemptions are not allowed.
- Immediate safety concerns should be discussed with the Sponsor immediately upon occurrence or awareness to determine if the patient should continue or discontinue study intervention.
- Adherence to the study design requirements, including those specified in the SoA, is essential and required for study conduct.
- All screening evaluations must be completed and reviewed to confirm that potential patients meet all eligibility criteria. The Investigator will maintain a screening log to record details of all patients screened and to confirm eligibility or record reasons for screening failure, as applicable. A patient who is rescreened is required to sign another ICF.
- Procedures conducted as part of the patient's routine clinical management (eg, blood count) and obtained before signing of the ICF may be utilized for screening or baseline purposes provided the procedures met the protocol-specified criteria and were performed within the timeframe defined in the SoA.

7.1 Safety Assessments

Safety objectives are identification of the MTD/RP2D of LC in combination with RT and TMZ and adjuvant TMZ.

7.1.1 *Definition of Evaluable for Safety*

All patients will be evaluable for toxicity from the time of their first study treatment.

7.1.2 *Assessments*

As detailed in [Section 7.2](#), safety assessments will consist of monitoring and recording all AEs and SAEs, the regular monitoring of hematology and blood chemistry, pregnancy testing (in WOCBP), regular measurement of vital signs, and the performance of physical/neurological examinations. ECGs and other cardiac monitoring may be performed as necessary.

Planned time points for all safety assessments are provided in the SoA ([Section 1.3](#)).

7.1.3 *Primary Safety Endpoints*

7.1.3.1 *Dose-Limiting Toxicity, Dose Escalation, and Assessment of Primary Endpoints*

Dose escalation will proceed within each cohort according to the scheme below ([Table 10](#)).

7.1.3.2 *Maximum Tolerated Dose and Recommended Phase 2 Dose*

Maximum Tolerated Dose: The MTD will be determined using a TITE-BOIN design as described in [Section 8](#).

Recommended Phase 2 Dose: The RP2D will be determined after reviewing the safety data at each dose level.

7.1.4 *Secondary Safety Endpoints*

7.1.4.1 *Physical Examinations*

- A complete physical examination will include, at a minimum, assessments of the cardiovascular, respiratory, gastrointestinal, and neurological systems. Height and weight will also be measured and recorded.
- A brief physical examination will include, at a minimum, assessments of the cardiopulmonary and neurological systems. New findings must be reported as AEs.
- Investigators should pay special attention to clinical signs related to previous serious illnesses.

7.1.4.2 *Vital Signs*

- Oral or tympanic temperature, pulse rate, respiratory rate, and systolic and diastolic blood pressure will be assessed.
- Blood pressure and pulse measurements will be assessed with a completely automated device. Manual techniques will be used only if an automated device is not available.
- Vital signs will be measured in a semisupine position after 5 minutes of rest and will include temperature, systolic and diastolic blood pressure, and pulse.

7.1.4.3 *Electrocardiograms*

Single 12-lead ECG will be obtained as outlined in the SoA (see [Section 1.3](#)) using an ECG machine that automatically calculates the heart rate and measures PR, QRS, QT, and QTc intervals. The Bazett formula will be used to calculate QTc intervals. Males with QTcB interval > 450 msec and females with QTcB interval > 460 msec should discontinue treatment with LC. Any patient with an increase from baseline in the QTcB interval > 15 msec should discontinue LC.

7.1.4.4 *Clinical Safety Laboratory Assessments*

- Clinical laboratory safety monitoring will occur as per the study calendar in [Section 1.3](#). Laboratory monitoring will be typical of that employed during standard therapy for newly diagnosed malignant gliomas.

- During weeks 2, 3 and 4 of CRT, a CBC with differential will be performed, including the parameters listed in [Table 12](#). During the post-CRT period when only LC is infused, weekly monitoring with a CBC with differential will continue.
- CMP will be evaluated on Day 15, Day 22, and then monthly, including the parameters listed in [Table 12](#).
- Because hemolytic anemia has been described, a baseline peripheral smear and LDH will be performed, and a repeat will be triggered if either of the following are observed:
 - 2-point decrease from baseline in Hgb
 - Hgb < 9 g/dL
- See [Section 9.3](#) (Appendix 3) for the list of clinical laboratory tests to be performed and to the SoA for the timing and frequency.
- The Investigator must review the laboratory report, document this review, and record any clinically relevant changes occurring during the study in the AE section of the CRF. The laboratory reports must be filed with the source documents.
- All laboratory tests with values considered clinically significantly abnormal during participation in the study or within 30 days after the last dose of LC should be repeated until the values return to normal or baseline or are no longer considered clinically significant by the Investigator or Medical Monitor.
- If such values do not return to normal/baseline within a period of time judged reasonable by the Investigator, the etiology should be identified and the Sponsor notified.
- All protocol-required laboratory assessments, as defined in [Section 9.3](#) (Appendix 3), must be conducted in accordance with the laboratory manual and the SoA.
- If laboratory values from nonprotocol-specified laboratory assessments performed at the institution's local laboratory require a change in patient management or are considered clinically significant by the Investigator (eg, SAE or AE or dose modification), then the results must be recorded in the CRF.

7.2 Adverse Events and Serious Adverse Events

The definitions of an AE or SAE can be found in [Section 9.4](#).

AEs will be reported by the patient (or, when appropriate, by a caregiver, surrogate, or the patient's legally authorized representative).

The Investigator and any qualified designees are responsible for detecting, documenting, and recording events that meet the definition of an AE or SAE and remain responsible for following up AEs that are serious, considered related to the study intervention or study

procedures, or that caused the patient to discontinue the study or study interventions (see [Section 6](#)).

7.2.1 Reporting Adverse Events

All AEs must be recorded in the electronic data capture system.

7.2.1.1 Adverse Event Description and Grade

The descriptions and grading in the NCI CTCAE version 5.0 will be used in the reporting of AEs. A change in grade will be reported as a separate AE. A copy of the CTCAE v 5.0 may be downloaded from

http://ctep.cancer.gov/protocolDevelopment/electronic_applications/ctc.htm.

7.2.1.2 Attribution of Adverse Events

The relationship of all AEs to each of the study drugs will be assessed as specified in [Table 8](#).

Table 8. Attribution of Adverse Events

Relationship	Definition
Definite	The AE is clearly related to the study treatment
Probable	The AE is likely related to the study treatment
Possible	The AE may be related to the study treatment
Unlikely	The AE is doubtfully related to the study treatment
Unrelated	The AE is clearly NOT related to the study treatment

AE = adverse event

For all AEs and each treatment (LC, TMZ, and RT), the Investigator will specify the corresponding relationship.

7.2.2 Time Period and Frequency for Collecting Adverse Event Information

All SAEs will be collected from the signing of the ICF until the last follow-up visit at the time points specified in the SoA ([Section 1.3](#)).

Adverse events will be collected from the start of treatment and followed for 30 days after the last dose of LC. Patients removed from the study for unacceptable AEs will be followed until resolution or stabilization of the AE ([Section 1.3](#), [Section 7.2.4](#), [Section 9.4.3](#)).

Medical occurrences that begin before the start of study intervention but after obtaining informed consent will be recorded on the Medical History/Current Medical Conditions section of the CRF, not the AE section.

All SAEs will be recorded and reported to the Sponsor or designee immediately and under no circumstance should this exceed 24 hr, as indicated in [Section 9.4](#) (Appendix 4). The Investigator will submit any updated SAE data to the Sponsor within 24 hr of it being available.

If the Investigator learns of any SAE, including a death, at any time after a patient has been discharged from the study, and the Investigator considers the event to be definitely, probably, or possibly related to the study intervention or study participation, the Investigator must promptly notify the Sponsor.

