4.1.1 Dose-Limiting Toxicities

The DLT assessment period for this study is 10 weeks: 6 weeks of concurrent LC and CRT, and 4 weeks of single-agent LC.

Hematological Toxicities

Hematological toxicities will be considered dose limiting if any of the following occur and complete blood counts (CBCs) and differentials were obtained according to the mandated schedule (CBC, differential, and platelet count drawn twice a week until the ANC \geq 1500/ μ L and platelet count \geq 100,000/ μ L):

- ANC < 500/ μ L
- Platelet count < 25,000/ μ L
- Grade 4 anemia
- Grade 3 hemolysis
- Febrile neutropenia
- Any hematological toxicity that prevents administration of \geq 80% of the planned LC dose

Grade 3 or 4 lymphopenia will not be considered a DLT.

Central Nervous System Toxicities

Central nervous system (CNS) toxicities are:

- \geq Grade 2 CNS ischemia

- \geq Grade 2 neurological toxicities that interfere with activities of daily living and do not resolve spontaneously or with steroids, anticonvulsants, or electrolyte correction within 2 weeks
- Symptomatic CNS hemorrhage of any grade

Nonhematological, Non-CNS Toxicities

Grade 3 and 4 nonhematological, non-CNS toxicities will be considered DLTs, with the following exceptions:

- Grade 3 nausea, vomiting, or diarrhea despite sufficient prophylaxis with a duration < 3 days
- Alopecia
- Grade 3 fatigue
- Grade 3 hyperglycemia that is reversible and without clinical symptoms
- Grade 3 electrolyte disturbances that are asymptomatic and reversible within 3 days, and do not re-occur upon continuing or re-initiation at the same dose
- Grade 3 or 4 hypophosphatemia, unless considered clinically relevant
- Grade 3 or 4 elevations in alkaline phosphatase
- Grade 3 hypertension that resolved to \leq Grade 2 hypertension within 1 week either spontaneously or upon implementation of antihypertensive therapy
- A first episode of deep venous thrombosis (DVT) or pulmonary embolism

Hepatic DLTs are:

- ALT or AST > 8 *upper limit of normal (ULN), regardless of duration
- ALT or AST > 5 *ULN and ≤ 8 *ULN that fails to return to \leq Grade 1 within 2 weeks despite medical intervention
- Total bilirubin > 5 *ULN
- ALT or AST > 3 *ULN and concurrent total bilirubin > 2 *ULN

FOR PATIENTS ON CONCURRENT TREATMENT, ANY DLT (AS DEFINED ABOVE) CAUSING DELAY IN TREATMENT OF OVER 7 DAYS WITHOUT RECOVERY TO A \leq GRADE 1 OR BASELINE STATUS WOULD RESULT IN TAKING THE PATIENT OFF CONCURRENT TREATMENT.

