4.1.6 Safety Monitoring

- The study will be overseen by an SRC composed of the Medical Monitor and 2 voting members from the Sidney Kimmel Comprehensive Cancer Center at Johns Hopkins. The SRC will convene to review data and discuss next steps at the end of every dose level (once all patients complete the 10-week evaluation period), the data have been cleaned, and the DLT outcomes are determined. In addition, the SRC will meet every 6 months at minimum, and as needed to review AEs. The Principal Investigator and study biostatistician will attend SRC meetings. The SRC will sign off on each dose level before activation of a new dose cohort or expansion of a dose cohort may begin.
- All women of childbearing potential (WOCBP) should be instructed to contact the Investigator immediately if they suspect they might be pregnant (eg, missed or late menstrual period) at any time during study participation. The Investigator must immediately notify the Medical Monitor in the event of a confirmed pregnancy in a patient participating in the study.
- The reason(s) for protocol therapy discontinuation, the reason(s) for study removal, and the corresponding dates must be documented in the Case Report Form (CRF).

- Adverse events will be followed for 30 days after the last dose of LC. Patients removed from the study for unacceptable AEs will be followed until resolution or stabilization of the AE.

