5.5 Study Interventions Administered

Table 5. Regimen Description - Concurrent CRT Period

Agent	Premedications / Precautions	Dose	Route	Schedule	Cycle Length
LC	Dexamethasone 4 mg IV Diphenhydramine 25 mg IV	Per treatment assignment	IV over 3 hr	Weekly: Weeks 1, 2, 3, 4, 5, 6	6 weeks
TMZ	No food 2 hr before and after dosing Antiemetic (eg, ondansetron, prochlorperazine) 30 minutes before dosing Stool softener PRN	75 mg/m ²	PO	Daily during term of RT	
RT		2 Gy	External beam therapy	Monday-Friday	

IV = intravenous; LC = liposomal curcumin; PO = per os (oral); PRN = pro re nata (as needed); RT = radiotherapy; TMZ = temozolomide

Table 6. Regimen Description - Post-CRT Period

Agent	Premedications / Precautions	Dose	Route	Schedule	Cycle Length
LC	Dexamethasone 4 mg IV Diphenhydramine 25 mg IV	Per treatment assignment	IV over 3 hr	Weekly: Weeks 7, 8, 9, 10	4 weeks

IV = intravenous; LC = liposomal curcumin

Table 7. Regimen Description - Adjuvant Period

Agent	Premedications / Precautions	Dose	Route	Schedule	Cycle Length
LC	Dexamethasone 4 mg IV Diphenhydramine 25 mg IV	Per treatment assignment	IV over 3 hr	Weekly: Adjuvant Cycles 1-6: Weeks 1, 2, 3, 4 of each cycle	4 weeks
TMZ	No food 2 hr before and after dosing	150-200 mg/m ² (Cycles 1-6)	PO	Daily	

Agent	Premedications / Precautions	Dose	Route	Schedule	Cycle Length
	Antiemetic (eg, ondansetron, prochlorperazine) 30 minutes before dosing Stool softener prn				

CRT = chemoradiotherapy; IV = intravenous; LC = liposomal curcumin; PO = per os (oral); PRN = pro re nata (as needed); TMZ = temozolomide

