6 DISCONTINUATION OF STUDY INTERVENTION AND PATIENT DISCONTINUATION/WITHDRAWAL

6.1 Discontinuation of Study Intervention

Patients who discontinue treatment with LC will continue to be followed for AEs for an additional 30 days after the last dose of LC and the last dose of TMZ, and then for progression-free survival and overall survival as described in [Section 4.1.6](#).

See the Schedule of Assessments (SoA) for data to be collected at the time of discontinuation of study intervention.

Discontinuation of study intervention for abnormal liver function should be considered by the Investigator when a patient meets one of the conditions outlined in the eligibility criteria of if the Investigator believes that it is in best interest of the patient.

If a clinically significant finding is identified (including, but not limited to changes from baseline in QTc interval after enrollment (using the Bazett formula [QTcB]), the Investigator or qualified designee will determine if the patient can continue in the study and if any change in patient management is needed. This review of the ECG printed at the time of collection must be documented. Any new clinically relevant finding should be reported as an AE. Males with QTcB interval > 450 msec and females with QTcB interval > 460 msec should discontinue treatment with LC. Any patient with an increase from baseline in the QTcB interval > 15 msec should discontinue LC.

See the SoA for data to be collected at the time of intervention discontinuation and follow-up and for any further evaluations that need to be completed.

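### Adverse event collection ends on two different dates, and under the LC-only rule it can close before the 10-week DLT window does

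*Protocol*

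**What the plan says.** Three places tie the end of adverse event (AE) follow-up to LC alone. SoA footnote 12 and Section 7.2.2 carry the same sentence: "Adverse events will be collected from the start of treatment and followed for 30 days after the last dose of LC". Section 4.1.6 says: "Adverse events will be followed for 30 days after the last dose of LC".

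Section 6.1 deals with patients who stop LC. They are to be "followed for AEs for an additional 30 days after the last dose of LC and the last dose of TMZ". That sentence then refers to Section 4.1.6 for progression and survival follow-up, and Section 4.1.6 is one of the places with the LC-only rule.

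The window behind the primary endpoint is fixed in Section 4.1.1: "The DLT assessment period for this study is 10 weeks: 6 weeks of concurrent LC and CRT, and 4 weeks of single-agent LC". Under Section 4.1, a patient with a DLT counts after a single LC dose. Under Section 4.1.5, a patient without one needs at least 8 of the 10 planned LC doses, plus minimum shares of radiotherapy (RT) and TMZ.

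Serious adverse events (SAEs) are collected for longer. Section 7.2.2 runs that collection from consent to the last follow-up visit.

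**The concern.** The two rules diverge for patients who stop LC early and carry on with RT and TMZ. The protocol itself can produce such patients. For example, an ECG is scheduled before treatment in Week 4, and the QTcB criteria in SoA footnote 7 and Section 6.1 can end LC without any mention of stopping RT or TMZ. A patient stopped at that ECG would have had the last LC dose at about Day 15.

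The DLT definitions in Section 4.1.1 are not limited to LC-related events, so a qualifying event after LC has stopped still counts if it falls within 10 weeks. If AE collection has already closed, a first DLT that is not serious has no stated route into the data. At stake is the DLT count that drives dose assignment and the choice of MTD.

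**Working it through.** **Inputs**
- DLT window: 6 weeks plus 4 weeks (Section 4.1.1).
- LC during chemoradiation: "Weekly: Weeks 1, 2, 3, 4, 5, 6" (Table 5), which the SoA places on Days 1, 8, 15, 22, 29 and 36, with ±3 days after Day 1.
- TMZ during chemoradiation: "Daily during term of RT" (Table 5). The last dose is assumed to fall at about Day 40 to 42.
- DLT risk weights: 20%, 30% and 50% by thirds of the window (Section 8.4.8).

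**Step 1, the window.** 6 × 7 + 4 × 7 = 70 days, which reproduces the stated 10 weeks.

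**Step 2, the LC-only rule.** End of collection = day of last LC dose + 30. Gap = 70 − end.

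| Last LC dose | Day | Collection ends | Days short of Day 70 |
|---|---|---|---|
| 1 | 1 | 31 | 39 |
| 2 | 8 | 38 | 32 |
| 3 | 15 | 45 | 25 |
| 4 | 22 | 52 | 18 |
| 5 | 29 | 59 | 11 |
| 6 | 36 | 66 | 4 |

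Dose 6 given at its latest, Day 39, ends collection on Day 69. Dose 7 at its earliest, Day 40, ends it on Day 70. The gap therefore affects patients whose last dose is one of doses 1 to 6.

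**Step 3, the Section 6.1 rule.** Read as the later of the two drugs, end = later of last LC and last TMZ dose + 30. Last TMZ on Day 40 gives Day 70, and Day 42 gives Day 72, so the window is covered. If both drugs have stopped by Day 39, the end is Day 69 or earlier and a gap remains.

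**Step 4, what happens to a missed event.** A patient whose last dose is dose 6 or earlier has at most 6/10 = 60% of LC doses, below the 80% needed. Without a recorded DLT the patient is non-evaluable and leaves both numerator and denominator. With it, the patient is evaluable with a DLT. Table 10 shows why one patient can matter. With none pending, 1 DLT in 3 means stay and 0 in 3 means escalate; 2 in 6 means stay and 1 in 6 means escalate. A changed decision also requires that the replacement patient has no DLT.

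**Step 5, worst-case illustration.** Each third is 70/3 = 23.33 days, with risk spread evenly within it (an assumption). The cumulative share F(d) is 0.2 + 0.3(d − 23.33)/23.33 in the middle third and 0.5 + 0.5(d − 46.67)/23.33 in the last. As a check, F(35) = 0.35 leaves 65% in the second half, matching Section 8.4.10.
- Last LC on Day 15: 1 − F(45) = 1 − 0.479 = 52%.
- Last LC on Day 22: 1 − F(52) = 1 − 0.614 = 39%.
- Last LC on Day 29: 1 − F(59) = 1 − 0.764 = 24%.

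**Step 6, how far apart the rules can be.** Take a patient who stops LC on Day 22 and completes six adjuvant cycles starting on Day 71. Cycle 6 starts on Day 71 + 5 × 28 = Day 211. With TMZ on Days 1 to 5 (SoA footnote 9), the last dose is on Day 215: 215 − 22 = 193 days, or 27.6 weeks. With daily TMZ (Table 7), the last dose is on Day 238: 238 − 22 = 216 days, or 30.9 weeks.

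**The case against.** The strongest reply is that Section 6.1 is the specific rule for LC discontinuers and the other three are general. On that reading, a patient who stops LC on Day 22 and finishes concurrent TMZ is covered to about Day 70 to 72. This is a reasonable reading, and it limits the gap to patients whose TMZ also stops early. It does not settle the matter, because nothing in the protocol says that Section 6.1 prevails and a site working from the SoA would apply footnote 12. The SoA marks AE assessment in Weeks 7 to 10, but the same footnote governs that row.

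Other safeguards shrink the exposure further:
- SAE collection continues, and Table 15 lists blood dyscrasias among events that would usually be considered serious. Many cytopenias would be caught this way.
- Hematological toxicity that prevents 80% of planned LC is itself a DLT under Section 4.1.1, so those patients are already counted.
- Patients removed for unacceptable AEs are followed to resolution or stabilization, and clinically significant laboratory values within 30 days of the last LC dose are repeated.

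None of these reliably captures a new, first, non-serious DLT that begins after closure.

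The percentages in Step 5 also need care. The weights were set for patients on the planned regimen. A patient off LC, in the weeks between concurrent and adjuvant TMZ, need not follow them.

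**Conclusion.** The contradiction is real and bears on the primary endpoint. Under the LC-only wording, collection stops 4 to 39 days short of the DLT window for last doses 1 to 6. Under Section 6.1 a gap remains only if TMZ also ends before about Day 40, given the assumption that concurrent TMZ otherwise runs to about Day 40 to 42. The exposed case is narrow: an early LC stopper not already counted as a DLT, with a first non-serious DLT late in the window. Any resulting bias in the DLT rate would be downward.

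A reader might infer that late DLTs will be missed and that the DLT count behind the MTD is therefore too low. The documents do not support that as fact: it depends on which rule sites follow, on when TMZ stops, and on a number of early LC stoppers that the protocol does not give. A reader might also take 52%, 39% and 24% as expected losses. They are a worst-case illustration only. The divergence of about 28 to 31 weeks in Step 6 concerns AE data generally, most of it after the DLT window.

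**What to change.** Reconcile SoA footnote 12 and Sections 4.1.6, 6.1 and 7.2.2 into one AE-collection rule consistent with Section 6.1. Say explicitly that where LC and TMZ end on different days, the later one counts. Add that AE and DLT collection never ends before the 10-week DLT window closes on Day 70, whenever LC or TMZ is stopped. The second sentence is needed because Section 6.1 alone leaves a gap when both drugs stop early.

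The adjuvant TMZ schedule should also be reconciled between SoA footnote 9 and Table 7, because it sets the end date under the Section 6.1 rule.

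The cost is a wording amendment and some extra weeks of AE recording in early LC stoppers. No dose or treatment rule needs to change for the AE-collection fix.
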